6.5.3. Prior and Concomitant Medications

Prior and concomitant medications will be classified using World Health Organization (WHO) Drug Dictionary codes and Anatomical Therapeutic Chemical (ATC) Classification for therapeutic indication. ATC Level 4 will be utilized as the drug classification. Prior and concomitant medications will be listed.

6.5.4. Vital Signs and Pulse Oximetry

Vital signs include systolic and diastolic blood pressures, respiratory rate, pulse, temperature. Vital signs and pulse oximetry will be listed.

6.5.5. Electrocardiograms

Triplet 12-lead ECGs will be obtained at Screening.

ECG data will be listed.

6.5.6. Echocardiograms/Multigated Acquisition Scan

An ECHO or MUGA scan will be performed at screening and at the end-of-treatment visit. For subjects receiving anthracycline in Induction Cycle 2, the ECHO or MUGA scan may be repeated within 48 hours prior to Cycle 2, Day 1 in subjects at increased risk for cardiotoxicity. ECHO data will be listed.

6.5.7. Physical Examinations

Physical examination will include body weight, height (at screening only) and a full neurological examination. These data will be presented in listing format.

6.5.8. ECOG Performance Status

ECOG PS score at each visit will be presented in a data listing.

7. PROTOCOL DEVIATIONS

All protocol deviations will be reviewed by the project team prior to unblinding to identify subjects with important protocol deviations.

All deviations from the study protocol will be available from the clinical team.

8. CHANGES IN THE PLANNED ANALYSES

As the study was terminated prior to the enrollment of 180 subjects, analyses of the efficacy and exploratory endpoints described in the protocol will not be conducted. These deviations will be documented in the final CSR.

10. PROPOSED TABLES, LISTINGS, AND FIGURES

Summary Tables

- 1 Subject Disposition
- 2 Demographics and Baseline Disease Characteristics
- 3 Exposure to Study Medication and Chemotherapy
- 4 Summary of Responses after Two Cycles of Chemotherapy
- 5 Summary of Treatment-Emergent Adverse Events by System Organ Class, Preferred Term, and Greatest Severity
- 6 Summary of Treatment-Related Adverse Events by System Organ Class and Preferred Term
- 7 Summary of Serious Treatment-Emergent Adverse Events by System Organ Class and Preferred Term
- 8 Summary of Treatment-Emergent Adverse Events by System Organ Class and Preferred Term
- 9 Summary of Treatment-Emergent Severity Graded Laboratory Abnormalities

Figures

- 1 Chemistry Parameters Over Time
- 2 Hematology Parameters Over Time

Data Listings

- 1 Subject Disposition
- 2 Treatment-Emergent Adverse Events
- 3 Treatment-Emergent Severity Graded Laboratory Abnormalities
- 4.1 Demographics
- 4.2 AML Diagnosis
- 5.1 Study Treatment - IV/Infusion Administration Details
- 5.2 Study Treatment - Oral Administration Details
- 6 Response Assessment after Two Cycles of Chemotherapy
- 7 Vital Signs, Height, and Weight
- 8 Electrocardiogram
- 9 Physical Examinations
- 10 ECOG Performance Status
- 11 Echocardiogram/MUGA for LVEF Assessment
- 12 General Medical History
- 13 Prior and Concomitant Medications
- 14 Prior Leukemogenic Agent Exposure

Appendix A: Programming Conventions

- Statistical software: The statistical analyses will be conducted with the SAS® software package version 9.4 or higher.
- Verification procedures: All analyses will be subject to formal verification procedures. Specifically, results will be verified utilizing independent programming prior to issuance of the draft statistical report. All documents will be verified by the lead statistician to ensure accuracy and consistency of analyses.
- Page orientation, margins, and fonts: Summary tables, listings, and figures will appear in landscape orientation. There should be a minimum of a 1" boundary on the upper (bound) edge, and a minimum of a 1.0" boundary on the remaining three edges. Output should be printed in Courier New with a point size of 8. Titles may be printed using a larger font (e.g., Arial point size 10).
- Identification of analysis population: Every summary table and figure should clearly specify the analysis population being summarized. Listings will be prepared for all subjects enrolled.
- Group headers: In the summary tables, the group headers will identify the treatment group and the within-group sample size for the indicated analysis population. Of note, the header's sample size does not necessarily equal the number of subjects actually summarized within any given summary module; some subjects in the analysis population may have missing values and thus may not be summarized.
- Suppression of percentages corresponding to null categories: When count data are presented as category frequencies and corresponding percentages, the percent should be suppressed when the count is zero in order to draw attention to the non-zero counts.
- Presentation of sample sizes: Summary modules should indicate, in one way or another, the number of subjects actually contributing to the summary statistics presented in any given summary module. As mentioned above, this may be less than the number of subjects in the analysis population.
 - ◆ In the quantitative modules describing continuous variables (and thus presenting sample size, means, and standard deviations), the sample size should be the number of non-missing observations.
 - ◆ For categorical variables that are presented in frequency tables, the module should present the total count in addition to the count in each category. Percentages should be calculated using this total as the denominator, and the percentage corresponding to the sum itself (that is, 100%) should be presented so as to indicate clearly to a reviewer the method of calculation.
- Sorting: Listings will be sorted by treatment group, patient number, and date, if applicable. If a listing is sorted in a different manner, a footnote will indicate as such.

- General formatting rules: Rounding for all variables will occur only as the last step, immediately prior to presentation in listings, tables, and figures. No intermediate rounding will be performed on derived variables. The standard rounding practice of rounding numbers ending in 0-4 down and numbers ending in 5-9 up will be employed.
- The presentation of numerical values will adhere to the following guidelines:
 - ◆ Raw measurements will be reported to the number of significant digits as captured electronically or on the CRFs.
 - ◆ Standard deviations will be reported to two decimal places beyond the number of decimal places the original parameter is presented.
 - ◆ Means, medians, first and third quartiles will be reported to one decimal place beyond the number of decimal places the original parameter is presented.
 - ◆ Calculated percentages will be reported with no decimals.
- Dates will be formatted as DDMMYY YYYY. Partial dates will be presented on data listings as recorded on CRFs.
 - Time will be presented according to the 24-hour clock (HHMM).

Appendix B: Programming Modified NCI-CTCAE Grading for Laboratory Abnormalities

Category	Analyte Name	CTCAE Term	Grade 1	Grade 2	Grade 3	Grade 4
Chemistry	Albumin	Hypoalbuminemia	<LLN - 3 g/dL	<3 - 2 g/dL	<2 g/dL	-
Chemistry	Amylase	Serum amylase increased	>ULN - 1.5 x ULN	>1.5 - 5.0 x ULN	>5.0 x ULN	-
Chemistry	Alanine Aminotransferase	Alanine aminotransferase increased	>ULN - 3.0 x ULN if baseline was normal; 1.5 - 3.0 x baseline if baseline was abnormal	>3.0 - 5.0 x ULN if baseline was normal; >3.0 - 5.0 x baseline if baseline was abnormal	>5.0 - 20.0 x ULN if baseline was normal; >5.0 - 20.0 x baseline if baseline was abnormal	>20.0 x ULN if baseline was normal; >20.0 x baseline if baseline was abnormal
Chemistry	Alkaline Phosphatase	Alkaline phosphatase increased	>ULN - 2.5 x ULN if baseline was normal; 2.0 - 2.5 x baseline if baseline was abnormal	>2.5 - 5.0 x ULN if baseline was normal; >2.5 - 5.0 x baseline if baseline was abnormal	>5.0 - 20.0 x ULN if baseline was normal; >5.0 - 20.0 x baseline if baseline was abnormal	>20.0 x ULN if baseline was normal; >20.0 x baseline if baseline was abnormal
Chemistry	Aspartate Aminotransferase	Aspartate aminotransferase increased	>ULN - 3.0 x ULN if baseline was normal; 1.5 - 3.0 x baseline if baseline was abnormal	>3.0 - 5.0 x ULN if baseline was normal; >3.0 - 5.0 x baseline if baseline was abnormal	>5.0 - 20.0 x ULN if baseline was normal; >5.0 - 20.0 x baseline if baseline was abnormal	>20.0 x ULN if baseline was normal; >20.0 x baseline if baseline was abnormal

Category	Analyte Name	CTCAE Term	Grade 1	Grade 2	Grade 3	Grade 4
Chemistry	Bilirubin (Total or Direct)	Blood bilirubin increased	>ULN - 1.5 x ULN if baseline was normal; > 1.0 - 1.5 x baseline if baseline was abnormal	>1.5 - 3.0 x ULN if baseline was normal; >1.5 - 3.0 x baseline if baseline was abnormal	>3.0 - 10.0 x ULN if baseline was normal; >3.0 - 10.0 x baseline if baseline was abnormal	>10.0 x ULN
Chemistry	Calcium Corrected for Albumin	Hypocalcemia	<LLN - 8.0 mg/dL	<8.0 - 7.0 mg/dL	<7.0 - 6.0 mg/dL	<6.0 mg/dL
		Hypercalcemia	>ULN - 11.5 mg/dL	>11.5 - 12.5 mg/dL	>12.5 - 13.5 mg/dL	>13.5 mg/dL
Chemistry/ Lipid Profile	Cholesterol	Cholesterol high	>ULN - 300 mg/dL	>300 - 400 mg/dL	>400 - 500 mg/dL; >500 mg/dL	>500 mg/dL
Chemistry	Creatine Kinase	CPK increased	>ULN - 2.5 x ULN	>2.5 x ULN - 5 x ULN	>5 x ULN - 10 x ULN	>10 x ULN
Chemistry	Creatinine	Creatinine increased	>ULN - 1.5 x ULN	>1.5 - 3.0 x baseline or >1.5 - 3.0 x ULN	>3.0 x baseline or >3.0 - 6.0 x ULN	>6.0 x ULN
Chemistry	GGT	GGT increased	>ULN - 2.5 x ULN if baseline was normal; 2.0 - 2.5 x baseline if baseline was abnormal	>2.5 - 5.0 x ULN if baseline was normal; >2.5 - 5.0 x baseline if baseline was abnormal	>5.0 - 20.0 x ULN if baseline was normal; >5.0 - 20.0 x baseline if baseline was abnormal	>20.0 x ULN if baseline was normal; >20.0 x baseline if baseline was abnormal

Category	Analyte Name	CTCAE Term	Grade 1	Grade 2	Grade 3	Grade 4
Chemistry	eGFR or CrCL	eGFR decreased/CrCL decreased	<LLN – 60 ml/min/1.73 m ²	<60 – 30 ml/min/1.73 m ²	<30 - 15 ml/min/1.73 m ²	<15 ml/min/1.73 m ²
Chemistry	Glucose	Hypoglycemia	<LLN - 55 mg/dL	<55 - 40 mg/dL	<40 - 30 mg/dL	<30 mg/dL
Chemistry	Lipase	Serum lipase increased	>ULN - 1.5 x ULN	>1.5 - 5.0 x ULN	>5.0 x ULN	-
Chemistry	Magnesium	Hypermagnesemia	>ULN - 3.0 mg/dL	-	>3.0 - 8.0 mg/dL mmol/L	>8.0 mg/dL
		Hypomagnesemia	<LLN - 1.2 mg/dL	<1.2 - 0.9 mg/dL	<0.9 - 0.7 mg/dL	<0.7 mg/dL
Chemistry	Potassium	Hyperkalemia	>ULN - 5.5 mmol/L	>5.5 - 6.0 mmol/L	>6.0 - 7.0 mmol/L	>7.0 mmol/L
		Hypokalemia	<LLN - 3.0 mmol/L	-	<3.0 - 2.5 mmol/L	<2.5 mmol/L
Chemistry	Sodium	Hypernatremia	>ULN - 150 mmol/L	>150 - 155 mmol/L;	>155 - 160 mmol/L	>160 mmol/L
		Hyponatremia	<LLN - 130 mmol/L	125-129 mmol/L	120-124 mmol/L	<120 mmol/L
Chemistry/ Lipid Profile	Triglycerides	Hypertriglyceridemia	150 mg/dL - 300 mg/dL	>300 mg/dL - 500 mg/dL	>500 mg/dL - 1000 mg/dL	>1000 mg/dL
Chemistry	Uric Acid	Hyperuricemia	>ULN	-	-	-

Category	Analyte Name	CTCAE Term	Grade 1	Grade 2	Grade 3	Grade 4
Chemistry	Bicarbonate or CO2	Blood bicarbonate decreased	<LLN	-	-	-
Hematology	Eosinophils	Eosinophilia	>ULN and > Baseline			
Hematology	Hemoglobin	Anemia	<LLN – 100 g/L	<100 – 80 g/L	<80 g/L	-
Hematology	Lymphocytes	Lymphocyte count decreased	<LLN - 800/mm3	<800 - 500/mm3	<500 - 200/mm3	<200/mm3
		Lymphocyte count increased	-	>4000/mm3 - 20,000/mm3	>20,000/mm3	-
Hematology	Neutrophils	Neutrophil count decreased	<LLN - 1500/mm3	<1500 - 1000/mm3	<1000 - 500/mm3	<500/mm3
Hematology	Platelets	Platelet count decreased	<LLN - 75,000/mm3	<75,000 - 50,000/mm3	<50,000 - 25,000/mm3	<25,000/mm3
Hematology	Leukocytes/ White Blood Cells	Leukocytosis	-	-	>100,000/mm3	-
		White blood cell decreased	<LLN - 3000/mm3	<3000 - 2000/mm3	<2000 - 1000/mm3	<1000/mm3

Category	Analyte Name	CTCAE Term	Grade 1	Grade 2	Grade 3	Grade 4
Coagulation	Activated partial thromboplastin time	Activated partial thromboplastin time prolonged	>ULN - 1.5 x ULN	>1.5 - 2.5 x ULN	>2.5 x ULN	-
Coagulation	Fibrinogen	Fibrinogen decreased Fibrinogen decreased from baseline	<1.0 - 0.75 x LLN; if abnormal, <25% decrease from baseline	<0.75 - 0.5 x LLN; if abnormal, 25 - <50% decrease from baseline	<0.5 - 0.25 x LLN; if abnormal, 50 - <75% decrease from baseline	<0.25 x LLN; if abnormal, 75% decrease from baseline; absolute value <50 mg/dL
Coagulation	International Normalized Ratio	INR increased	>1.2 - 1.5	>1.5 - 2.5	>2.5	-

Note: Values noted as 'abnormal' at baseline should be outside the normal range in the direction of the toxicity grade.

Note: In cases where the lower limit of normal (LLN) or upper limit of normal (ULN) of a given laboratory value falls in the Grade 2 or higher range of the scale, the toxicity will be graded at the higher value (i.e., a lymphocyte test has a LLN of 600/mm³, any value of 600/mm³ will be considered as a Grade 2 abnormality).

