No. of treated patients, n (%)	26 (100)
Any Grade ≥ 3 TEAE	21 (81)
Nonhematologic TEAEs/laboratory abnormalities	
Device-related infection	3 (12)
Blood bilirubin increased	5 (19)
Sinusitis	2 (8)
Hyponatremia	3 (12)
Hypophosphatemia	4 (15)
Alanine aminotransferase increased	2 (8)
Alkaline phosphatase increased	2 (8)
Hypokalaemia	3 (12)
Sepsis	2 (8)
Hematologic TEAEs/laboratory abnormalities	
Febrile neutropenia	13 (50)
Anemia	9 (35)
Platelet count decreased	8 (31)
White blood cell count decreased	9 (35)
Neutrophil count decreased	6 (23)
Neutropenia	4 (15)
Thrombocytopenia	3 (12)
Lymphocyte count decreased	5 (19)
Leukopenia	2 (8)

Abbreviations: TEAE, treatment-emergent adverse events.

CONFIDENTIAL

Protocol KB-ENTO-3001 v4.0 Global
(Amendment 3.0 Global)

In summary, both the spectrum and frequency of TEAEs reported in association with the combination of ENTO and 7+3 induction and cytarabine consolidation were generally as expected for the underlying disease and treatment with intensive induction/consolidation chemotherapy. Rash, indirect hyperbilirubinemia, and transaminase elevations are specifically attributed to ENTO (Investigator's Brochure, [Section 6.2.5](#)). Toxicities observed to date with ENTO plus intensive induction/consolidation can be readily monitored and managed with close attention to standard safety assessments (eg, blood counts, electrolytes, liver function studies, fluid and electrolyte balance, and careful surveillance, treatment, and follow-up for infectious complications). The type and frequency of safety assessments described for the proposed study have been modeled to conform with those employed in Study GS-US-339-1559 and are in accordance with National Comprehensive Cancer Network (NCCN) supportive care recommendations. All are generally consistent with the standards of care for newly diagnosed AML patients undergoing intensive induction and consolidation chemotherapy.

Considering measures that are undertaken to minimize the risk to prospective study subjects, the potential risks identified in association with the combination of ENTO and intensive induction and consolidation chemotherapy are justified by the anticipated benefits that may be afforded to subjects with *NPM1*-mutated AML.

More detailed information about the known expected adverse drug reactions of ENTO may be found in the Investigator's Brochure ([Section 6.1.2.2](#); [Section 6.2](#)).

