Includes electrolytes (sodium, potassium, chloride, total CO₂ and/or bicarbonate, calcium, phosphate), liver function studies (AST, ALT, total and direct bilirubin), lactate dehydrogenase, alkaline phosphatase, blood urea nitrogen (BUN) or serum urea, creatinine, uric acid, glucose, amylase, and lipase. Include total creatine phosphokinase at Screening, Day 14 of each Induction cycle, and at the End of Study Treatment. At times not designated in [Table 7](#), monitor electrolytes, LFTs, BUN, creatinine, uric acid, and phosphate in accordance with institutional care standards until the risk of tumor lysis syndrome has abated. For subjects receiving nephrotoxic antimicrobial agents, closer monitoring of renal function throughout the period of hospitalization is recommended, consistent with institutional standards of care.

Coagulation Parameters:

Includes prothrombin time, activated partial thromboplastin time and international normalized ratio. Perform coagulation panel twice per week during induction. For subjects with evidence of disseminated intravascular coagulation, coagulation parameters including fibrinogen should be monitored until resolution.

Hepatitis/HIV Serologies:

Includes HBsAg, anti-HBs, anti-HBc, anti-HCV, and anti-HIV. Patients who are seropositive for HBsAg are excluded. HIV + patients may be considered for enrollment if they meet all criteria outlined in [Section 5.2](#) and for whom the risk of adverse interactions between anti-retroviral therapy and the study medication is assessed as minimal to none.

Urinalysis:

Includes dipstick evaluation for pH, glucose, protein, blood, leukocyte esterase and microscopic evaluation for red and white blood cells. After Screening, perform urinalysis as clinically indicated.

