ⁱ Includes hemoglobin, hematocrit, white blood cell (WBC) and platelet counts, and WBC differential (neutrophils, bands, lymphocytes, monocytes, eosinophils, basophils, blasts). At times not designated in Table 7, monitor CBC and WBC differential in accordance with institutional care standards until ANC is $\geq 1.0 \times 10^9/L$ or persistent leukemia is documented. Monitor platelet counts at times designated in Table 7 and at other times, per institutional care standards until the platelet count is $\geq 100 \times 10^9/L$ or persistent leukemia is documented. Monitor CBC and platelet count twice weekly during consolidation and at other times, as clinically indicated.

^j Includes electrolytes (sodium, potassium, chloride, total CO₂ and/or bicarbonate, calcium, phosphate), liver function studies (aspartate aminotransferase [AST], alanine aminotransferase [ALT], total and direct bilirubin), lactate dehydrogenase (LDH), alkaline phosphatase, blood urea nitrogen [BUN] or serum urea, creatinine, uric acid, glucose, amylase, and lipase. Include total creatine phosphokinase (CPK) at Screening, Day 14 of each induction cycle, and End of Study Treatment. At times not designated in Table 7, monitor electrolytes, LFTs, BUN, creatinine, uric acid, and phosphate in accordance with institutional care standards until the risk of tumor lysis syndrome has abated. For subjects receiving nephrotoxic antimicrobial agents, closer monitoring of renal function throughout the period of hospitalization is recommended, consistent with institutional standards of care.

^k Includes prothrombin time, activated partial thromboplastin time and international normalized ratio. Perform coagulation panel twice per week during Induction. For subjects with evidence of disseminated intravascular coagulation (DIC), coagulation parameters including fibrinogen should be monitored in accordance with institutional care standards until resolution.

^l Includes dipstick evaluation for pH, glucose, protein, blood, leukocyte esterase and microscopic evaluation for red and white blood cells. After Screening, perform urinalysis as clinically indicated.

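### SAP Appendix B grades calcium only after an albumin correction that the listed chemistry panel cannot supply, and phosphate, which is in the panel, has no planned laboratory summary

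*SAP*

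**What the plan says.** The chemistry panel is the same in three places: Protocol 8.6.4, Protocol Table 7 footnote j, and footnote j of the schedule in SAP 2.2. The SAP footnote opens "Includes electrolytes (sodium, potassium, chloride, total CO₂ and/or bicarbonate, calcium, phosphate), liver function studies". The liver studies named are AST, ALT, and total and direct bilirubin. The protocol list then continues through "lactate dehydrogenase, alkaline phosphatase, blood urea nitrogen (BUN) or serum urea, creatinine, uric acid, glucose, amylase, and lipase". Creatine phosphokinase is added at selected visits ("Include total creatine phosphokinase at Screening, Day 14 of each Induction cycle, and at the End of Study Treatment"). Albumin appears in none of the three lists.

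SAP Appendix B sets the grading limits. Its only calcium entry, for both hypocalcemia and hypercalcemia, is "Calcium Corrected for Albumin". It also has an albumin row ("Hypoalbuminemia"). The SAP gives no correction formula. There is no phosphate row.

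SAP 4.4.4 derives treatment-emergent laboratory toxicities by program from the laboratory CRF pages. SAP 6.5.2 refers to Appendix B for the grading and summarises frequencies and shifts by treatment group. The parameters that 6.5.2 names for figures include neither calcium nor phosphate. In SAP Section 10, Table 9 and Listing 3 are restricted to graded abnormalities, and no listing of raw laboratory results is proposed.

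Protocol Table 3 (Section 2.4), for the 26 treated subjects of Study BAML-16-001-S6A, includes "Hypophosphatemia" among Grade 3 or higher treatment-emergent events, at 4 (15%).

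**The concern.** SAP Section 2 states that the document exists to produce safety analyses for an abbreviated study report, so laboratory safety is one of the few results the trial will deliver. A programmed derivation can grade only what its table defines and its data supply. For calcium the table requires an input that the panel does not list. The programmer must then either leave calcium out or substitute an uncorrected value that the SAP does not authorise. For phosphate the table has no entry, and the figures and proposed listings do not make up for it.

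Phosphate is not an arbitrary analyte here. Protocol 8.6.4 names it among the tests to be followed while the risk of tumor lysis lasts, and it ranked high among non-hematologic events in an earlier ENTO cohort.

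**Working it through.** **1. Reproduce the plan's figure.** From Protocol Table 3, 4/26 = 15.4%, shown as 15. Of the nine non-hematologic rows, blood bilirubin increased is highest (5/26 = 19.2%) and hypophosphatemia is second. Hyponatremia, hypokalemia and device-related infection follow at 3/26 = 11.5% each. The exact 95% interval for 4/26 is 4.4% to 34.9%.

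**2. Compare the panel with Appendix B.**
- In the panel without a usable grading row: calcium as measured, phosphate, chloride, urea and LDH.
- Of these, urea nitrogen and LDH are among the parameters plotted under SAP 6.5.2. Calcium, phosphate and chloride are not. The documents give no particular reason for interest in chloride.
- Graded but not in the panel: albumin, cholesterol, GGT, magnesium and triglycerides. (eGFR or creatinine clearance can be derived from creatinine.)

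**3. Follow each analyte to the outputs.**
- Calcium: without albumin there is no corrected value, hence no grade and no entry in Table 9, Listing 3 or the shift summary. It is not in Figure 1 either.
- Phosphate: no row, hence no grade under any data, and the same absences follow.

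**4. Does the calcium rule change a grade?** Illustration with assumed values: measured calcium 7.8 mg/dL, albumin 2.5 g/dL, reference albumin 4.0 g/dL, and an assumed correction of 0.8 mg/dL per g/dL.
- Corrected calcium = 7.8 + 0.8 × (4.0 − 2.5) = 9.0 mg/dL.
- Under the Appendix B limits, 7.8 is Grade 2 (below 8.0, down to 7.0). A value of 9.0 is normal if the laboratory's lower limit is 9.0 or less.
- The move out of Grade 2 does not depend on 0.8. Any factor above (8.0 − 7.8)/(4.0 − 2.5) = 0.13 takes the value past 8.0.

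**5. How likely is a relevant phosphate event here?** Assume the S6A rate applies and that 15 subjects randomized 1:1 give 7 or 8 on ENTO. The chance of at least one Grade 3 or higher event is 1 − (22/26)^n:
- n = 7: 69%
- n = 8: 74%
- n = 15 (if the rate applied to everyone): 92%

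**6. Sodium bands.** The hyponatremia grades in Appendix B run to 130, then 125 to 129, then 120 to 124 mmol/L. Results of 129.5 or 124.5 fall in no band. The hypernatremia grades in the same table have no such gap. Appendix A allows rounding only at presentation, so rounding before grading does not close it.

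**The case against.** Several counterarguments carry weight.

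- **The CRF is not available.** SAP Section 2 sends the reader to it for data collection, and Protocol 8.6.4 allows for tests outside the protocol. Albumin may have been recorded at some sites. This stands: the supported statement is that albumin is not in the listed panel, not that it was never collected.
- **The adverse-event route remains.** Protocol 8.6.4 requires clinically significant laboratory changes to be recorded as adverse events, and SAP 6.5.1 tabulates these by preferred term. The S6A figure is itself an adverse-event count. This also stands. What is lost is the systematic summary of changes that no investigator judged reportable.
- **The phosphate signal is modest.** Seven rows of Table 3 exceed it, six of them hematologic, and neutropenia ties with it at 4. It leads the next non-hematologic rows by one patient. In the 53-subject Phase 1b/2 study, Section 2.4 does not name it among Grade 3 or higher non-hematologic events above 10%.
- **A grading row may not have been available.** The documents do not reproduce NCI-CTCAE, so whether it offers a numeric phosphate grade cannot be checked here. The remedy therefore should not depend on one.
- **The SAP promises that all data will be listed** (4.4.5 and Section 6). That would cover raw calcium and phosphate, but Section 10 proposes no such listing.

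A reader might also infer that the rows for tests outside the panel do harm, or that a shared "Bilirubin (Total or Direct)" row lets the expected indirect rise hide a direct bilirubin signal. The documents support neither. A row without data yields no toxicity. The bilirubin label does not say that the two results are pooled, and SAP 6.5.2 plots total, direct and indirect bilirubin separately.

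**Conclusion.** The point holds in limited form. On the listed panel, the calcium rule cannot be run as written. Phosphate, although collected, appears in no proposed laboratory table, figure or listing and would surface only as an investigator-reported adverse event. This rests on the panel as listed being what was recorded; albumin on the CRF would rescue calcium but not phosphate.

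The size is small. The trial stopped in November 2022 with 15 randomized subjects, SAP 4.1 plans no formal testing, and no efficacy, alpha or sample-size figure is touched. The 69% to 74% chance of at least one event is an illustration built on 4 of 26 and an assumed arm size, not a forecast. The sodium gap matters only if laboratories report decimals, which the documents do not show.

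The edits are still worth making, because one stated rule lacks its input and one safety analyte is left unsummarised.

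**What to change.** - **Calcium:** grade albumin-corrected calcium where albumin was recorded, and state the formula. Otherwise summarise measured calcium, labelled uncorrected, with a footnote that low albumin can produce apparent hypocalcemia.
- **Figures:** add calcium and phosphate to the chemistry parameters in SAP 6.5.2.
- **Phosphate:** report worst post-baseline phosphate by arm, stating which direction counts as worst. This needs no grading threshold.
- **Sodium (minor):** write the hyponatremia bands as <130 to 125 and <125 to 120 mmol/L, to match the hypernatremia bands.

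The cost is a few SAP edits and minor programming, with no new procedures. Adding albumin to the blood draws is no longer an option in a terminated study. The downside is that uncorrected calcium may overstate hypocalcemia, which is why the label and footnote are needed.
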